1.5 Correlative Studies

Molecular profiling including exome and transcriptome sequencing of baseline or multiplex immunohistochemistry of archived tissue specimens will allow us to identify predictive markers of treatment response. As this testing will be performed on tissue obtained as a component of routine care, there is no additional risk to the patient. Tissue sampling at the time of progression is encouraged but not required. Tissue at progression may undergo similar testing to identify markers or mechanisms of resistance.

Archival tissue will also be examined using the Xerna™ TME Panel which is a RNA-based gene expression assay to classify patients based on the biology of the tumor microenvironment (TME).

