2.3 Exploratory Objectives

2.3.1 To explore the objective response rate as assessed by iRECIST of combination axitinib, bavituximab, and avelumab in patients with advanced HCC.

- 2.3.2 To explore the utility of tissue and/or serum-based markers as predictors of therapy response.

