9.0 CORRELATIVES/SPECIAL STUDIES

The goal of the planned laboratory correlative studies is to assess genetic mechanisms of immunotherapy resistance. Analyses will be performed on tissue specimens collected as a component of routine clinical practice, and thus no additional specimen collection solely for research purposes is required.

Archival or baseline tumor tissue will be genomically characterized by MI Profile (Caris Life Sciences). This will allow us to assess whether mutations, copy number alterations, and RNA signatures may be associated with different clinical outcomes.

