10.3 Data Analyses

Objective response rate, and disease control rate with corresponding 2-sided 95% CIs will be estimated using the Clopper-Pearson method. Kaplan-Meier methods will be used to estimate medians and 95% CIs for duration of response, overall survival, and progression-free survival. Survival outcomes will be calculated from Day 1 of Cycle 1. Descriptive statistics will be used to analyze AEs described according to the NCI CTCAE v5.0. Clinically significant laboratory abnormalities will be described as well. Serious adverse events will be summarized, including a causality assessment. The number of treatment cycles and doses administered will be summarized using descriptive statistics.

Associations between molecular features and tumor response will be analyzed using the Fisher-exact test with Benjamini-Hochberg multiple-testing correction. Cox regression models will be used to assess for associations between overall survival or progression-free survival and exploratory and correlative measures.

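### Section 10.3 names only Fisher's exact test for molecular features against tumor response, so any feature measured on a continuous scale must be grouped first; no cut-point is given, and grouping usually costs power.

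*Combined protocol and SAP*

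**What the plan says.** The combined protocol and SAP gives one method for this question, in section 10.3: "Associations between molecular features and tumor response will be analyzed using the Fisher-exact test with Benjamini-Hochberg multiple-testing correction". It names no rank test, t test or logistic model for response. It gives no cut-point rule, no false discovery rate level and no number of features. The next sentence uses a method that accepts continuous covariates, but for other endpoints: "Cox regression models will be used to assess for associations between overall survival or progression-free survival and exploratory and correlative measures".

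The features are described in two places. Section 1.5 plans "Molecular profiling including exome and transcriptome sequencing of baseline or multiplex immunohistochemistry of archived tissue specimens", plus an RNA-based panel that sorts patients into tumor microenvironment (TME) classes. Section 9.0 asks whether "mutations, copy number alterations, and RNA signatures may be associated with different clinical outcomes". The aim served is exploratory objective 2.3.2: "To explore the utility of tissue and/or serum-based markers as predictors of therapy response".

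**The concern.** Fisher's exact test works on a contingency table. It fits a mutation that is present or absent, a called copy number alteration, or a TME class. It cannot take an expression level, a signature score or a quantitative staining measurement until someone has divided the patients into groups.

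Three things follow for such features. Information within each group is lost. The p-value can take only a few values, which matters with at most 29 patients and a multiplicity correction to pass. And because no cut is fixed in advance, it could be chosen after the responses are known, which Benjamini-Hochberg does not correct for. At stake is the chance that objective 2.3.2 finds a real marker in tissue the trial will already hold.

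**Working it through.** **Inputs from section 10.2.** At most 29 evaluable patients, response rates of 34% (alternative) and 14% (null), and rejection at 7 or more responses. The stated design reproduces: continuing with at least 2 of 14 and rejecting with at least 7 of 29 gives an exact type I error of 0.0973 and power of 0.9002. The plan states no power for the molecular analyses, so there is no figure of that kind to reproduce. Responder counts used here: 0.34 × 29 = 9.9, so 10; 7, the rejection boundary; and 0.14 × 29 = 4.1, so 4.

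**Assumptions, because the plan gives none.** All 29 patients have a usable value. The feature is normal with equal spread and shifted upward by 1.0 SD in responders. The cut is at the sample median. Tests are two-sided at 0.05, unadjusted.

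**Tests.** With h patients in the high group and r responders, P(a responders in the high group) = C(h,a) × C(29−h, r−a) / C(29,r). Fisher's two-sided p adds every outcome no more probable than the one observed. The comparator is the exact Wilcoxon rank-sum test on the uncut values.

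**Power by simulation (100,000 data sets per cell).**

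| Responders | High/low | Fisher | Wilcoxon | Loss (points) |
|---|---|---|---|---|
| 10 | 14/15 | 46% | 67% | 21 |
| 7 | 14/15 | 48% | 57% | 9 |
| 10 | 15/14 | 23% | 67% | 44 |
| 7 | 15/14 | 17% | 57% | 40 |

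**Why one patient matters so much.** Take 7 responders, with C(29,7) = 1,560,780.

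- Split 14/15, 6 of 7 high: the outcomes 6, 7 and 0 count, so p = (45,045 + 3,432 + 6,435) / 1,560,780 = 0.035. This is significant.
- Split 15/14, 6 of 7 high: the outcomes 6, 7, 1 and 0 count, so p = (70,070 + 6,435 + 45,045 + 3,432) / 1,560,780 = 0.080. This is not.

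The two splits swap roles for a marker that is lower in responders. Any single rule for the odd patient therefore favors markers in one direction and penalizes those in the other.

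**Very few responders.** With 4 responders and a 14/15 split, Fisher's test loses nothing against Wilcoxon up to about 1.0 SD. With 15/14, even 4 of 4 high gives p = (C(15,4) + C(14,4)) / C(29,4) = (1,365 + 1,001) / 23,751 = 0.0996, so an upward marker can never reach 0.05.

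**Discreteness or lost information?** With 10 responders, Fisher's true null rejection rate is 0.021 and Wilcoxon's is 0.050. Holding Wilcoxon to p ≤ 0.0209 (achieved size 0.018) on the 14/15 split leaves 50% against Fisher's 46% at 1.0 SD, and 32% against 31% at 0.8 SD. So about 67 − 50 = 17 of the 21 points reflect Fisher's conservatism. With 7 responders on the same split it is different: Fisher's upper-tail null probability is (45,045 + 3,432) / 1,560,780 = 0.031, above the 0.025 that Wilcoxon can spend per tail, yet power is still 9 points lower. There, the cut itself is the cause.

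**After Benjamini-Hochberg.** With 7 responders, the smallest median-split Fisher p is C(14,7) / C(29,7) = 3,432 / 1,560,780 = 0.0022. The smallest Wilcoxon p is 2 / 1,560,780 = 1.3 × 10⁻⁶. At an assumed 5% false discovery rate, one feature passes alone only if p ≤ 0.05/m, so m ≤ 0.05 / 0.0022, or about 22 features. With an assumed 100 features, 100 × 0.0022 / 0.05 = 4.4, so at least 5 must sit at that minimum together.

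**The case against.** The strongest reply is that much of the planned material suits Fisher's test. Mutations and the TME class are categorical. Section 9.0 speaks of copy number alterations, which are normally called as present or absent. AFP appears as a laboratory test (sections 5.1.9 and 5.2.1), not as a molecular feature. The plan does not say how transcriptome or immunohistochemistry data will be summarized, so a continuous scale is possible but not stated. This stands, and it limits the point to features that are in fact measured on a continuous or ordinal scale. A reader might infer that most of the molecular analysis is affected; the documents do not show that.

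A second reply is that the comparison is uneven, because Fisher's test runs below its nominal level. That also stands for 10 responders, as shown above. A reader might infer that the whole gap is information thrown away by the cut; it is not. But an analyst who follows the plan bears the conservatism too, so the gain from changing the test is still real.

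A third reply is that the analysis is exploratory, with no power target and no decision attached. That is correct and sets the severity. It does not argue against an improvement that costs almost nothing.

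**Conclusion.** The point holds in limited form. For continuous or ordinal features against response, section 10.3 leaves only a test that requires grouping, and it gives no cut-point. Under the stated assumptions at 1.0 SD, the loss against a rank test is 9 to 21 points with the favorable split and 40 to 44 points with the unfavorable one, for 7 and 10 responders.

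A reader might take one of these figures as a fixed cost of the plan. The documents do not support that: the loss moves with the split, the responder count and the effect size, and it can vanish with 4 responders and the favorable split. A reader might also infer that the cut test can hardly ever pass the Benjamini-Hochberg step. That depends on the panel size and the false discovery rate, and the plan states neither; in a panel of up to about 22 features, a single marker can pass at 5% even with 7 responders.

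The primary endpoint, the stopping rule and the Cox analyses of overall and progression-free survival are untouched. This is a cheap improvement of low severity.

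**What to change.** Replace the sentence on response in section 10.3 with wording such as: 'Categorical molecular features (mutation status, called copy number alterations, TME class) will be tested against objective response with Fisher's exact test. Features measured on a continuous or ordinal scale (for example transcript expression, RNA signature scores, quantitative immunohistochemistry) will be compared between responders and non-responders with the exact Wilcoxon rank-sum test, without dichotomization. The Benjamini-Hochberg procedure will be applied across both sets of tests together.'

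The change should be made before the molecular data are analyzed against response. It costs one sentence and a standard routine in the analysis code, with no new patients, samples or assays. The small downside is that a rank test yields no ready-made high/low cut-point; groups can still be shown descriptively. Stating the false discovery rate level in the same edit would also let readers judge what the correction demands.

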11.0 STUDY MANAGEMENT

11.1 Conflict of Interest

Any investigator who has a conflict of interest with this study (patent ownership, royalties, or financial gain greater than the minimum allowable by their institution, etc.) must have the conflict reviewed by the UTSW COI Committee and IRB according to UTSW Policy on Conflicts of Interest. All investigators will follow the University conflict of interest policy.

11.2 Institutional Review Board (IRB) Approval and Consent

It is expected that the IRB will have the proper representation and function in accordance with federally mandated regulations. The IRB must approve the consent form and protocol.

In obtaining and documenting informed consent, the investigator should comply with the applicable regulatory requirement(s), and should adhere to Good Clinical Practice (GCP) and to ethical principles that have their origin in the Declaration of Helsinki.

Before recruitment and enrollment onto this study, the subject will be given a full explanation of the study and will be given the opportunity to review the consent form. Each consent form must include all the relevant elements currently required by the FDA Regulations and local or state regulations. Once this essential information has been provided to the subject and the investigator is assured that the subject understands the implications of participating in the study, the subject will be asked to give consent to participate in the study by signing an IRB-approved consent form.

Prior to a patient's participation in the trial, the written informed consent form should be signed and personally dated by the subject and by the person who conducted the informed consent discussion.

11.3 Required Documentation (for multi-site studies)

Before the study can be initiated at any sub-site, the following documentation must be provided to the UTSW Clinical Research Office.

- A copy of the official IRB approval letter for the protocol and informed consent
- IRB membership list or Federal-wide Assurance letter
- CVs and medical licensure for the principal investigator and any associate investigators who will be involved in the study
- Form FDA 1572 appropriately filled out and signed with appropriate documentation (NOTE: this is required if UTSW holds the IND. Otherwise, the affiliate Investigator's signature on the protocol is sufficient to ensure compliance)
- A copy of the IRB-approved consent form
- CAP and CLIA Laboratory certification numbers and institution lab normal values
- Executed clinical research contract
- Signed Monitoring Plan

11.4 Data Management and Monitoring/Auditing

REDCap is the UTSW SCCC institutional choice for the electronic data capture of case report forms for SCCC Investigator Initiated Trials. REDCap will be used for electronic case report forms in accordance with Simmons Comprehensive Cancer Center requirements, as appropriate for the project

In order to facilitate remote source to case report form verification, the Simmons Comprehensive Cancer Center study team will require other institutions participating in this trial as sub-sites to enter data into the selected EDC system and upload selected de-identified source materials when instructed.

Trial monitoring will be conducted according to the study specific monitoring plan. This will be conducted no less than annually and refers to a regular interval review of trial related activity and documentation performed by the UTSW Simmons Cancer Center Gastrointestinal Disease-Oriented Teams (GI DOT), which includes but is not limited to accuracy of case report forms, protocol compliance, timeliness and accuracy of Velos entries and AE/SAE management and reporting. Documentation of trial monitoring will be maintained along with other protocol related documents and will be reviewed during internal audit.

Toxicity and dose escalation reviews will be performed in real-time by the GI DOT and DSMC. These reviews will be documented by distributing reports of the findings to the members of the GI DOT and investigators.

The UTSW Simmons Comprehensive Cancer Center (SCCC) Data Safety Monitoring Committee (DSMC) is responsible for monitoring data quality and patient safety for all UTSW SCCC clinical trials. As part of that responsibility, the DSMC reviews all serious adverse events and UPIRSOs in real time as they are reported and reviews adverse events on a quarterly basis. The quality assurance activity for the Clinical Research Office provides for periodic auditing of clinical research documents to ensure data integrity and regulatory compliance. A copy of the DSMC plan is available upon request.

The SCCC DSMC meets quarterly and conducts annual comprehensive reviews of ongoing clinical trials, for which it serves as the DSMC of record. The Quality Assurance Coordinator (QAC) works as part of the DSMC to conduct regular audits based on the level

of risk. Audit findings are reviewed at the next available DSMC meeting. In this way, frequency of DSMC monitoring is dependent upon the level of risk. Risk level is determined by the DSMC Chairman and a number of factors such as the phase of the study; the type of investigational agent, device or intervention being studied; and monitoring required to ensure the safety of study subjects based on the associated risks of the study. Protocol-specific DSMC plans must be consistent with these principles.

11.5 Adherence to the Protocol

Except for an emergency situation in which proper care for the protection, safety, and well-being of the study subject requires alternative treatment, the study shall be conducted exactly as described in the approved protocol.

11.5.1 Exceptions (also called single-subject exceptions or single-subject waivers): include any departure from IRB-approved research that is *not due to an emergency* and is:

- intentional on part of the investigator; or
- in the investigator's control; or
- not intended as a systemic change (e.g., single-subject exceptions to eligibility [inclusion/exclusion] criteria)
 - Reporting requirement***: Exceptions are non-emergency deviations that require *prospective* IRB approval before being implemented. Call the IRB if your request is urgent. If IRB approval is not obtained beforehand, this constitutes a major deviation. For eligibility waivers, studies which utilize the SCCC-DSMC as the DSMC of record must also obtain approval from the DSMC prior to submitting to IRB for approval.

11.5.2 Emergency Deviations: include any departure from IRB-approved research that is necessary to:

- avoid immediate apparent harm, or
- protect the life or physical well-being of subjects or others
 - Reporting requirement***: Emergency deviations must be promptly reported to the IRB within 5 working days of occurrence.

11.5.3 Serious Noncompliance (formerly called **major deviations** or **violations**): include any departure from IRB-approved research that:

- Increase risk of harm to subjects; and/or
- adversely affects the rights, safety, or welfare of subjects (any of which may also be an unanticipated problem); and/or
- adversely affects the integrity of the data and research (i.e., substantially compromises the integrity, reliability, or validity of the research)
 - Reporting requirement***: Serious Noncompliance must be promptly reported to the IRB within 5 working days of discovery.

11.5.4 Continuing Noncompliance: includes a pattern of repeated noncompliance which continues **after** initial discovery, including inadequate efforts to take or implement corrective or preventive action within a reasonable time frame.

- Reporting requirement***: Continuing Noncompliance must be promptly reported to the IRB within 5 working days of discovery.

11.5.5 Noncompliance (that is neither serious nor continuing; formerly called minor deviations) any departure from IRB-approved research that:

- Does not meet the definition of serious noncompliance or continuing noncompliance
 - Reporting requirement*:** Noncompliance that is neither serious nor continuing should be tracked and summarized the next IRB continuing review, or the notice of study closure- whichever comes first.

*Reporting Requirements reflect UTSW HRPP/IRB guidelines; participating sites should follow the reporting guidelines for their IRB of record.

11.6 Amendments to the Protocol

Should amendments to the protocol be required, the amendments will be originated and documented by the Principal Investigator. A summary of changes document outlining proposed changes as well as rationale for changes, when appropriate, is highly recommended. When an amendment to the protocol substantially alters the study design or the potential risk to the patient, a revised consent form might be required.

The written amendment, and if required the amended consent form, must be sent to the IRB for approval prior to implementation.

11.7 Record Retention

Study documentation includes all Case Report Forms, data correction forms or queries, source documents, Sponsor-Investigator correspondence, monitoring logs/letters, and regulatory documents (e.g., protocol and amendments, IRB correspondence and approval, signed patient consent forms).

Source documents include all recordings of observations or notations of clinical activities and all reports and records necessary for the evaluation and reconstruction of the clinical research study.

Government agency regulations and directives require that the study investigator retain all study documentation pertaining to the conduct of a clinical trial. In the case of a study with a drug seeking regulatory approval and marketing, these documents shall be retained for at least two years after the last approval of marketing application in an International Conference on Harmonization (ICH) region. In all other cases, study documents should be kept on file until three years after the completion and final study report of this investigational study.

11.8 Obligations of Investigators

The Principal Investigator is responsible for the conduct of the clinical trial at the site in accordance with Title 21 of the Code of Federal Regulations and/or the Declaration of Helsinki. The Principal Investigator is responsible for personally overseeing the treatment of all study patients. The Principal Investigator must assure that all study site personnel, including sub-investigators and other study staff members, adhere to the study protocol and all FDA/GCP/NCI regulations and guidelines regarding clinical trials both during and after study completion.

The Principal Investigator at each institution or site will be responsible for assuring that all the required data will be collected and entered onto the Case Report Forms. Periodically, monitoring visits may be conducted and the Principal Investigator will provide access to his/her original records to permit verification of proper entry of data. At the completion of the study, all case report forms will be reviewed by the Principal Investigator and will require his/her final signature to verify the accuracy of the data.

13.0 APPENDICES

Appendix A: Drug diary

SUBJECT DOSING DIARY

SITE STAFF INSTRUCTIONS (prior to providing to subject):

- Complete the header and footer of each page (one page per week) of the diary. The subject should be instructed to complete the dosing diary table(s).
- Complete the contact details at the bottom of this cover page with the name and phone number for the best contact person for subject inquires.
- It is important to train the subject on correct completion of this diary. For the first dose on Cycle 1 Day 1 training must be completed.
- Ensure the subject understands this diary should be completed daily and brought to the clinic at each visit along with all used bottles of Axitinib.

SUBJECT INSTRUCTIONS

Diary Instructions:

- This is a "diary" that you will use to keep track of daily dose amounts, when you take your doses. Each page represents 1 week of dosing, so you should complete 4 pages for each 28-day cycle.
- It is important that you fill out this diary (using pen) every time you take a dose. Record the day of the week, date, time, and number of tablets taken for each dosing.
- **You must bring this diary and all used bottles to the clinic at each visit.** It is important that you keep the diary and bottles in a safe place where they will not be lost.

Dosing Instructions:

- Axitinib should be taken at approximately the same time(s) each day and may be administered without regard to meals or other medications.
- Tablets should not be crushed, split, or dissolved – swallow whole.
- If you miss a dose of Axitinib you must follow these guidelines:
 - A missed dose may be taken late, up to 3 hours before the next scheduled dose that day. Otherwise, skip and resume dosing with next scheduled dose.
 - If you vomit at any time after taking a dose, do not "make it up". Continue taking Axitinib as scheduled.
 - Record all doses – including missed or vomited – on the dosing diary.
- ****If a surgery or an interventional procedure is planned, you will need to discuss this with your doctor because Axitinib may need to be temporarily held for safety reasons.****
- If you have any questions, please contact the clinic staff at:

Name / Study Coordinator

Telephone

**For Clinical Trial Use Only. Keep out of reach of children.
Maintain tablets in original bottles.**

Confidential

Dosing Diary Version 2 - 20Apr2022
IRB # 2022-0116

Year _____
Cycle ____ Week ____

STU-2022-0116 – SCCC#01522 – Protocol Number Pending

Subject ID:	
Dose Assigned:	_____ mg BID (Twice Daily)

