- 3.2.24 Prisoners or subjects who are involuntarily incarcerated.
- 3.2.25 History of leptomeningeal disease.
- 3.2.26 Symptomatic or clinically active brain metastases.

- 3.2.27 Pregnant or nursing (lactating) women, where pregnancy is defined as the state of a female after contraception and until the termination of gestation, confirmed by a positive hCG laboratory test.
- 3.2.28 Has dual active HBV infection (HBsAg (+) and /or detectable HBV DNA) and HCV infection (anti-HCV Ab(+) and detectable HCV RNA) at study entry.
- 3.2.29 Known prior or suspected hypersensitivity to study drugs or any component in their formulations.
- 3.2.30 Current use or anticipated need for drugs that are known strong CYP3A4/5 inducers, including their administration within 10 days prior to patient receiving the first study treatment, eg, phenobarbital, rifampin, phenytoin, carbamazepine, rifabutin, rifapentin, clevidipine, St John's wort.
- 3.2.31 Patients with 2+ proteinuria on urine dipstick analysis and confirmed to have ≥ 2 grams of protein in a 24-hour urine collection.
- 3.2.32 Current use or anticipated need for treatment with drugs or foods that are known strong CYP3A4/5 inhibitors, including their administration within 10 days prior to patient receiving the first study treatment, (eg, grapefruit juice or grapefruit/grapefruit-related citrus fruits, ketoconazole, miconazole, itraconazole, voriconazole, posaconazole, clarithromycin, telithromycin, indinavir, saquinavir, ritonavir, nelfinavir, amprenavir, fosamprenavir, nefazodone, lopinavir, troleandomycin, mibefradil, and conivaptan). The topical use of these medications (if applicable), such as 2% ketoconazole cream, is allowed.

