- 4.1.4 Axitinib dosage form and packaging: Axitinib will be supplied by Pfizer as 1 mg and 5 mg film-coated tablets for oral administration in light-resistant high-density polyethylene (HDPE) bottles with desiccant.
- 4.1.5 Axitinib administration: Axitinib will be provided in quantities appropriate for the study visit schedule. A qualified staff member will provide the study treatment via a unique container number. Axitinib will be dispensed every 4 weeks or as otherwise indicated.

Axitinib will be administered orally BID at approximately the same time in the morning and evening on a continuous dosing schedule. Axitinib tablets are to be taken approximately 12 hours apart and may be administered without regard to meals or avelumab and bavituximab administration. Tablets must not be crushed, split, or dissolved, and patients should be instructed to swallow the study medication whole without manipulation or chewing of the medication prior to swallowing.

Patients must be instructed that if they miss a dose or vomit any time after taking a dose, they must not "make it up" with an extra dose, but instead resume subsequent doses as prescribed. Any missed dose may be taken late, up to 3 hours, before the next scheduled dose of that day, otherwise, it should be skipped and dosing resumed with subsequent doses as prescribed. Patient must be instructed to record all doses (missed or vomited doses or extra doses) in a dosing diary supplied by the site.

- 4.1.6 Bavituximab dosage form and packaging: Bavituximab is supplied OncXerna as a sterile, preservative-free solution with 10 mM acetate at pH 5.0 and diluted with 0.9% saline (normal saline) to a final volume of 100 mL.
- 4.1.7 Bavituximab administration: Bavituximab will be administered weekly on Days 1, 8, 15 and 22 of the 28-day cycle.

Infusion preparation and administration are to be performed as follows:

1. Draw up the volume of a vial using a sterile syringe attached to an appropriate needle (a vented spike or other appropriate transfer device may be used). Fill treatment into a sterile glass bottle or plastic IV bag.
2. Using aseptic techniques, repeat procedure until the calculated volume has been put into the container. Bring the final volume to 100 mL using 0.9% Sodium Chloride Injection, USP.
3. Administer through a low protein binding 0.2-micrometer in-line filter (placed as proximal to the patient as practical).

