8.0 DRUG/TREATMENT INFORMATION

8.1 Axitinib

- Other names for the drug(s): Inlyta
- Classification - type of agent: Targeted therapy
- Mode of action: Selective inhibitor of VEGFR-1, 2, and 3
- Storage and stability: Axitinib must be stored at controlled room temperature (between 15-30 C) or as specified in the product label.
- Protocol dose: 5 mg BID at approximately the same time in the morning and evening on a continuous dosing schedule. Axitinib tablets are to be taken approximately 12 hours apart and may be administered without regard to meals. Tablets must not be crushed, split, or dissolved, and patients should be instructed to swallow the study medication whole without manipulation or chewing of the medication prior to swallowing. A dosing card will be provided to the patients to provide guidance for the correct use of axitinib.
- Route of administration for this study: oral
- Availability: provided by Pfizer

- Side effects: The most common ($\geq 20\%$) adverse reactions observed following treatment with axitinib were diarrhea, hypertension, fatigue, decreased appetite, nausea, weight decreased, dysphonia, palmar-plantar erythrodysesthesia, hemorrhage, hypothyroidism, vomiting, proteinuria, cough, and constipation. See Section 7.1.4 and the axitinib Investigator's Brochure for additional information on expected treatment related AEs.

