8.1.1 Return and Retention of Study Drug

Patients will be required to return to the investigational site all bottles of axitinib every 4 weeks (at the end of each cycle) during the planned visit at the site. The number of remaining axitinib tablets will be documented and recorded at each clinic visit. The patient diary may also be used to support this part of the axitinib accountability process.

The sponsor or designee will provide guidance on the destruction of unused investigational product. If destruction is authorized to take place at the study site, the investigator must ensure that the materials are destroyed in compliance with applicable environmental regulations, institutional policy, and any special instructions provided by Pfizer, and all destruction must be adequately documented.

- ### **8.1.2**
- A dosing card will be provided to the patients to provide guidance for the correct use of axitinib. Patients must be instructed that if they miss a dose or vomit any time after taking a dose, they must not "make it up" with an extra dose, but instead resume subsequent doses as prescribed. Any missed dose may be taken late, up to 3 hours before the next scheduled dose of that day, otherwise, it should be skipped and dosing resumed with subsequent doses as prescribed. Patient must be instructed to record all doses (missed or vomited doses or extra doses) in a dosing diary supplied by the site.

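### The patient dosing diary says axitinib can be taken without regard to other medicines, which is wider than sections 4.1.5 and 8.1 allow: a minor wording correction

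*Combined protocol and SAP*

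**What the plan says.** Three places tell someone how freely axitinib may be taken.

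- **Appendix A, Dosing Instructions (read by the patient):** "Axitinib should be taken at approximately the same time(s) each day and may be administered without regard to meals or other medications".
- **Section 4.1.5 (read by site staff):** the tablets "may be administered without regard to meals or avelumab and bavituximab administration".
- **Section 8.1, protocol dose:** "Axitinib tablets are to be taken approximately 12 hours apart and may be administered without regard to meals".

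Elsewhere the protocol restricts what may be taken with axitinib. Exclusion 3.2.30 covers "Current use or anticipated need for drugs that are known strong CYP3A4/5 inducers", and 3.2.32 does the same for strong inhibitors, including grapefruit. Section 4.3 carries medications barred by the exclusions into the active treatment period. Section 4.3.1 states that strong inhibitors are not permitted, with topical use allowed.

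Section 8.1 also mentions a second patient-held item: "A dosing card will be provided to the patients to provide guidance for the correct use of axitinib". Its text is not in the documents.

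**The concern.** Axitinib is the one study drug that patients take at home, twice a day. The diary is the instruction they have in hand, and they do not have section 4.1.5 beside it to show that the other medications meant are two infusions given in clinic. Taken at face value, the phrase tells them that other medicines need not be considered.

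The protocol treats some of those medicines as important. Section 7.1.3 says CYP3A4/5 inhibitors and grapefruit may raise axitinib concentrations and strong inducers may lower them. Where an interacting drug cannot be avoided, 4.3.1 and 7.1.3 point to roughly halving axitinib for an inhibitor, and 7.1.3 to adjusting the dose for a strong inducer. At stake is whether a patient would start such a medicine between visits without asking. No statistical quantity is involved.

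**Working it through.** No calculated figure in the plan bears on this point, so the check is a comparison of texts.

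**Step 1. Scope of the permission in each place.**

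| Place | Reader | Meals | Study infusions | Any other medicine |
|---|---|---|---|---|
| Section 8.1 | Site | Yes | Not mentioned | Not mentioned |
| Section 4.1.5 | Site | Yes | Yes | Not mentioned |
| Diary, Appendix A | Patient | Yes | Only within the general phrase | Yes, without limit |

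Nothing in the body of the protocol extends the permission to medicines in general. The diary is the current version in the appendix, so superseded text does not explain the difference.

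**Step 2. Does the wider scope reach anything the protocol restricts?** Yes. Strong inducers (3.2.30) and strong inhibitors (3.2.32) are excluded at entry. Section 4.3 continues those bars during treatment, and 4.3.1 repeats the one on inhibitors.

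**Step 3. The two ways to read the diary sentence.**

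- *As timing advice:* axitinib need not be spaced from meals or from other medicines. There is then no conflict with the bars in Step 2. Only the mismatch with 4.1.5 and 8.1 remains.
- *As advice about what may be combined:* other medicines do not matter. This conflicts with 3.2.30, 3.2.32, 4.3 and 4.3.1.

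The sentence opens with the time of day, which favours the first reading. Nothing in it rules out the second.

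**Step 4. What else stands between the patient and a barred medicine?**

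- The exclusions remove patients with current use or foreseeable need before enrolment.
- Medication review takes place at screening, on Days 1, 8, 15 and 22 of each cycle, and at end of treatment (5.2.1 to 5.2.3 and the Time and Events Table).
- The diary gives a clinic contact for questions.

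During treatment the reviews are nominally 7 days apart (8 − 1 = 15 − 8 = 22 − 15 = 7, and 29 − 22 = 7 to the next Day 1). A medicine started at home could therefore go unnoticed for about a week, or 7 × 2 = 14 axitinib doses. This is the nominal interval between reviews. It says nothing about how often such a thing would happen.

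**Step 5. Effect on the analysis.** The response endpoint, the two-stage design with up to 29 evaluable patients, and the methods in 10.3 do not depend on this sentence.

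**The case against.** The strongest reply is that the protocol uses this form of words for timing only. Sections 4.1.5 and 8.1 both free axitinib from any link to meals, yet 3.2.32 and 4.3.1 bar grapefruit. If the phrase permitted every item it mentions, those two sections would contradict the grapefruit bar as well. As timing advice, moreover, the diary is not wrong. No section asks for axitinib to be spaced from a permitted medicine, such as an HBV antiviral (3.1.11) or an antihypertensive (Table 2).

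This stands as evidence of what was intended, and it is why the point is minor. It does not settle what a patient will understand, because the patient does not read the sections that reveal the convention. Using the 4.1.5 scope would lose the timing advice for permitted medicines, but the body of the protocol does not give that advice either.

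A reader might infer more than the documents support in four ways:

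- *That the plan nowhere warns patients about interactions or grapefruit.* The dosing card is not reproduced and the consent pages were removed, so this cannot be checked.
- *That altered exposure could add events to the six-patient safety lead-in or lower the response rate.* The chain is conceivable, but no frequency of use, change in exposure or event rate can be derived from the documents.
- *That the number of drugs named in the two exclusions measures the problem.* Both lists are examples, so a count gives only their length.
- *That this is the only diary line looser than the body.* It is not. The diary says axitinib may need to be held around surgery or an interventional procedure, whereas 4.3.3 requires interruption at least 24 hours before.

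**Conclusion.** The mismatch is certain: the diary's permission is wider than 4.1.5 and wider still than 8.1. The sentence was probably meant as timing advice, and on that reading it breaks no bar. Its plain wording can still mislead a patient about medicines that the protocol prohibits or adjusts the dose for.

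The point is minor. Exclusion at entry, scheduled medication review and the clinic contact line reduce the risk, though none of them corrects the sentence itself. The size cannot be put as a rate of use or harm. Endpoint, sample size and analysis are unaffected.

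The conclusion assumes that some patients will rely on the diary's wording without checking with the clinic. It assumes nothing about what the dosing card or consent form says. If either already carries a clear warning, the practical risk is smaller, but the diary would still not match the protocol.

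**What to change.** In the diary's first dosing instruction, replace the words *or other medications* with *or your avelumab and bavituximab infusions*. This brings the patient's text into line with 4.1.5.

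Then check the dosing card and the consent form. If neither already says so, add one line to the diary, for example: *Ask the study team before you start any new medicine or supplement, and avoid grapefruit.*

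The cost is one revised diary (now Version 2) through the IRB. Nothing in the endpoint, sample size or analysis has to change.
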